## **7.0 MEDICAL DEVICE REPORTING**

On a routine basis, the third party entity will report to Mentor pre-specified events (e.g., death of a participant) involving MemoryGel and Mentor saline breast implants consistent with Medical Device Reporting (MDR) standards. All data, including MDR-reported data, will be part of the annual reports for the MemoryGel™ PAS.

## **8.0 SURVEY METHODOLOGY**

There are no longer requirements for annual participant questionnaires. See the previous protocol amendment (Amendment 1) for the methodology for collecting questionnaire data for MemoryGel™ PAS.

## **9.0 DATA COLLECTION**

This section describes the proposed data collection strategy and management plan for MemoryGel™ PAS.

### **Physician Evaluation Data (MemoryGel Participants Only)**

MemoryGel participants will be evaluated for reasons for reoperation, with or without removal, and reasons for removal by their surgeons at unscheduled/interim visits. The physician will submit the completed complications form via Internet or mail to the third party study entity for entry into the study database.

Because of the mobility and general good health of participants who will be receiving MemoryGel implants, at the participant's request, Mentor or third party delegate will provide patients with listings of regional surgeons who may be available to perform reoperation evaluations on any MemoryGel participant in the study.

There are no longer requirements for annual participant questionnaires. See the previous protocol amendment (Amendment 1) for the survey data collection details for MemoryGel™ PAS.

### **9.1 Quality Assurance**

The proposed MemoryGel™ PAS modes of data collection will be subject to strict quality assurance procedures.

### **9.2 Management**

Mentor will employ a third party study entity that will develop systems and structures to effectively and efficiently manage the data collection for MemoryGel™ PAS. The third party study entity will have experience in creating, maintaining, and management of systems that ensure timely production of study data. Quality Assurance must be built into the management structure and into methods for collecting data and delivering data files with their documentation.

## **10.0 MEDICAL RECORDS**

The postapproval study was originally designed to address the issues identified in [Table 1 and](#), in certain circumstances (see protocol Amendment 1), medical records of MemoryGel participants were to be obtained to confirm information provided by the participant. Medical records will be not obtained under this amended protocol.

## 11.0 STATISTICAL CONSIDERATIONS

### 11.1 Statistical Analyses

This section describes the analyses to be conducted under this protocol amendment. It is important to recognize that this study is observational. As a result, data from this study can be used only to establish association, not causality, and data should be evaluated within the context of the broader composite of literature relating to the study endpoints. All of the analyses under this protocol amendment will be based on the MemoryGel participants only.

#### Complications/Reoperations

The cumulative incidence of key local complications (explantation, and reoperation) for women with MemoryGel implants will be estimated based on physician evaluations for the MemoryGel participants using Kaplan-Meier methodology to estimate the time to the first occurrence of the complication or reoperation. Ninety-five percent confidence intervals will be computed. In addition, the relative frequency of reasons for reoperation will be computed.

Under the original protocol, the purpose of the inclusion of the saline participants was to serve as concurrent controls for assessing rheumatologic and neurologic signs. Rheumatological and neurological data will not be collected under this protocol amendment.

Mentor will generate the following final clinical study reports for submission to FDA:

- One final report at the end of the study phase conducted under Amendment 1, including data from beginning of the study through the end of the study phase under Amendment 1. The statistical analysis will be conducted as described in the original protocol (see below).
- One final report at the end of the study phase conducted under Amendment 2, including data from the execution of Amendment 2 to the end of the study. The statistical analysis will be conducted as described above.

The original analyses conducted to address each of the postapproval study's original objectives are identified below and correspond to issues outlined in Table 1:

*It is important to recognize that this study is observational. As a result, data from this study can be used only to establish association, not causality, and data should be evaluated within the context of the broader composite of literature relating to these issues. All of the analyses, except for the analyses of rheumatological and neurological signs and symptoms, will be based on the MemoryGel participants only.*

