## 2.0 OBJECTIVES

This amended protocol will collect data on secondary procedures/reoperations. The issues to be addressed include the following:

- What are the Kaplan-Meier (KM) implant removal and reoperation rates over time?
- What are the reasons for reoperation over time?

The postapproval study was originally designed to address the issues identified in Table 1, which includes reoperation data as described above.

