### 3.0 DESIGN

This protocol amendment includes participant follow-up only. Study enrollment has been closed since 15 Oct 2008 and no new study participants will be enrolled. Data collection will only take place if a participant requires a secondary procedure/reoperation. There are no longer requirements for scheduled office visits or annual participant questionnaires. The study is currently in year 7 and follow-up will continue through 10 years or until the National Breast Implant Registry opens for data collection, whichever occurs first.

As in the original protocol, there will be no concurrent controls needed as a source of comparison for secondary procedures/reoperations (see local complications category in original study design Tables 1 and 2). Thus, saline implant participants will not have data collected under this amended protocol.

Mentor will employ third party study entities that will be responsible for the following: (1) collecting data from surgeons; (2) entering data into and administering the study database; (3) generating follow-up reports as well as datasets; (4) meeting with Mentor on a regular basis; and (5) analyzing the study data. Mentor will be responsible for: (1) IRB approval; (2) monitoring third party entities; (3) analyzing the study data; and (4) periodic reporting to FDA.

The postapproval study was originally designed as follows:

*MemoryGel™ PAS uses a current cohort design of the first 41,900 women receiving Mentor's MemoryGel implants, with 10 years of follow-up. It will include augmentation, reconstruction, and revision patients, each in their naturally occurring proportions at participating study sites.*

*For the purpose of assessing rheumatological and neurological signs and symptoms, there also will be 1,000 saline breast implant patients from the participating surgeons' practices who will serve as concurrent controls. Concurrent control participants will be enrolled by approximately 30 physicians who routinely use saline implants. These investigative sites will be selected with the objective of obtaining the desired number of controls in an appropriate time frame, e.g. roughly the same time frame as the recruitment of MemoryGel subjects. These sites are to enroll all saline subjects meeting the specified eligibility criteria until 1,000 controls are recruited into this study.*

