## 4.0 PARTICIPANT POPULATION

Study enrollment has been closed since 15 Oct 2008 and no new study participants will be enrolled. Approximately 1,700 centers participated in the study and enrollment included 41,451 MemoryGel participants and 1,039 saline participants. As of the last annual study report (dated Nov 2013), the follow-up rates through six years were 21.8% for MemoryGel participants and 15.0% for saline participants.

The postapproval study was originally designed with the following eligibility criteria:

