			 Suspected Rupture/Deflation
REASON FOR REOPERATION (Patient Request/Other):			
			 Patient wishes change in shape/size/style
			 Need for Biopsy
			 Staged Reconstruction
			 Tumor
			 Other, specify: _____
Reporting Physician (Principal Investigator) Signature			Date:    
			DD                  MMM                  YYYY
V2 - 04FEB2015	Confidential CRF	Page 4	

MENTOR	MGPAS Amendment 2												
 MGPAS Amendment 2 #085      Discontinuation #099													
Participant No:	Site No:	Participant Initials:											

 
  	 	 	 	
 
					
 
  	 	 	 	
 
					
 
  	 	 	
 
			
DISCONTINUATION													
Date of Discontinuation:													

 
  	 	 	
 
 DD                      MMM                      YYYY													
Reason for Discontinuation: (Mark one only)													
 Completed 10-year study													
 Consent withdrawn													
 Lost to follow-up													

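### No analysis by indication is specified for the reoperation and removal Kaplan-Meier rates, so a pooled rate could drift in either direction if risk and loss both differ by indication

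*Combined protocol and SAP*

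**What the plan says.** Amendment 2 keeps two objectives. The first (Section 2.0) asks "What are the Kaplan-Meier (KM) implant removal and reoperation rates over time". The matching analysis in Section 11.1, Complications/Reoperations, covers "The cumulative incidence of key local complications (explantation, and reoperation) for women with MemoryGel implants", "using Kaplan-Meier methodology to estimate the time to the first occurrence of the complication or reoperation", with 95% confidence intervals and one set of relative frequencies for the reasons for reoperation. The analysis set is stated once: "All of the analyses under this protocol amendment will be based on the MemoryGel participants only". Neither the amended text nor the original Complications/Reoperations text reproduced after it names strata, covariates or weights.

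On the make-up of the cohort, Section 3.0 says of the original design: "It will include augmentation, reconstruction, and revision patients, each in their naturally occurring proportions at participating study sites". The eligibility criteria and footnotes in Section 4.0 separate augmentation from reconstruction and, within each, primary from revision surgery. On size and retention, Section 4.0 reports that "enrollment included 41,451 MemoryGel participants and 1,039 saline participants" and that "the follow-up rates through six years were 21.8% for MemoryGel participants and 15.0% for saline participants". Retention is not split by indication. The reoperation form in Section 16.0 lists "Staged Reconstruction" among the reasons for reoperation.

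**The concern.** The four indications are different surgical populations, and the sponsor's own form carries a reason for reoperation that belongs to reconstruction. If rates differ between indications, one curve for all women is an average whose value depends on the case mix, and a woman with a given indication cannot read her own rate from it.

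Loss to follow-up adds a second problem. At each time point, Kaplan-Meier weights the groups by the women still under observation. If the groups lose women at different speeds and also have different risks, those weights move away from the enrolled mix and the pooled curve follows them. The overall retention figure cannot show whether this has happened.

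Other endpoints in the original analysis plan receive standardization or regression adjustment for patient characteristics (for example connective tissue disease, cancer, offspring outcomes, and signs and symptoms). Reoperation and removal, the only rate endpoints kept under Amendment 2, receive none.

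**Working it through.** **Figures in the plan.** No target, precision or expected rate is stated for the reoperation or removal curves. The original sample size addresses rare disease incidence (Section 11.2). It reproduces: the year-end sum of (1 − 0.035k) for k = 1 to 10 is 8.075 person-years per woman, and 338,000 / 8.075 = 41,858, against the stated 41,900. It has no bearing on this point.

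**Inputs from the documents.** 41,451 MemoryGel women enrolled; 21.8% overall follow-up through six years.

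**Assumed inputs, because the documents give none by indication.** Two groups, A (lower risk) and B (higher risk), in a 70:30 mix. Constant reoperation hazards of 2% and 6% a year. Exponential loss, with six-year retention f in each group, so the loss hazard is c = −ln(f)/6. Time runs from implantation to year 10.

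**True values.**
- Group A: 1 − exp(−0.02 × 10) = 18.1%.
- Group B: 1 − exp(−0.06 × 10) = 45.1%.
- Enrolled-mix average: 0.70 × 18.1% + 0.30 × 45.1% = 26.2%.

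**Pooled Kaplan-Meier.** Its large-sample limit at ten years is 1 − exp(−∫h(t)dt), where h(t) = Σ wᵢλᵢSᵢ(t) / Σ wᵢSᵢ(t) and Sᵢ(t) = exp(−(λᵢ + cᵢ)t). Integrated numerically:

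| Retained at 6 years, A v B | Overall retention | Pooled 10-year rate | Shift from 26.2% |
|---|---|---|---|
| 21.8% v 21.8% | 21.8% | 26.2% | 0 |
| 25% v 15% | 22.0% | 24.2% | −2.0 points |
| 20% v 26% | 21.8% | 27.5% | +1.3 points |
| 15% v 40% | 22.5% | 31.5% | +5.3 points |
| 10% v 50% | 22.0% | 34.7% | +8.5 points |

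All five patterns are close to the reported 21.8% overall, so that figure cannot tell them apart. Curves estimated by group return 18.1% and 45.1% in every row, provided loss is non-informative within each group.

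**Sensitivity to the loss model.** If loss is linear to year 6 and then stops, the four unequal rows become 24.9%, 27.1%, 29.7% and 32.1%. The shifts are smaller but keep their direction.

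**A second set of assumptions.** Three groups at 70/15/15 with ten-year rates of 25%, 45% and 40% have a mix average of 30.3%. With overall retention held at 21.8%, the pooled rate is 28.8% when the groups retain 25%, 14.3% and 14.3%, and 34.8% when they retain 12%, 44.7% and 44.7%. If all three rates are 25%, the pooled rate stays at 25.0% whatever the loss pattern.

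**Does precision require pooling?** 0.218 × 41,451 is about 9,036 women. At a 25% rate, the simple binomial 95% half-width is 1.96 × √(0.25 × 0.75 / 9,036) = 0.9 points for all of them, and 1.96 × √(0.25 × 0.75 / 904) = 2.8 points for a group holding 10% of them. This is only an order of magnitude, since it ignores the time course of censoring. It does not suggest that the groups are too small to report.

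**The case against.** The objective asks for rates over time in the cohort, and the cohort was enrolled in its natural mix on purpose. An overall curve answers that question, and with loss unrelated to indication it answers it without bias. This stands.

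A reader might go further and infer that the planned rate is wrong, describes none of the women, or has a late part driven by a changing mix. The documents do not support that. They report no reoperation rate, share or retention by indication, so neither of the two required differences is shown. The staged-reconstruction reason shows one source of reoperation specific to reconstruction, but not how large it is. A reader might also expect the shift to be upward. It can go either way, and with modest differences in loss it is about one point.

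The illustration runs from implantation. Section 11.1 limits the Amendment 2 report to data from execution of that amendment onward, Section 3.0 puts the study in year 7, and data are collected only when a reoperation occurs. The table therefore does not describe that report, and its figures should not be attached to it.

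Section 11.1 does not exclude results by indication; it specifies none. Staged reconstruction is already a coded reason and will appear in the relative frequencies, so what is missing there is only a version of the Kaplan-Meier rate. The Amendment 2 form has no indication field, so indication must come from enrolment data. That is plausible, because the age criterion for augmentation depends on it, but the present document does not show the field.

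**Conclusion.** The point holds in a conditional form. What is established from the text is that Section 11.1 specifies no analysis by indication for removal or reoperation in a cohort of mixed indications with 21.8% overall follow-up through six years. It follows that the pooled curve estimates the enrolled-mix average if loss is unrelated to indication, and departs from it if risk and loss both differ by indication.

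The size is not known. Under the two-group assumptions it runs from 2.0 points below to 8.5 points above a true 26.2%, and it is zero if either risk or loss is equal across groups. The change is worth making: it concerns the first of two remaining objectives, costs little, and replaces an untestable reliance on equal loss across indications with a weaker assumption within each.

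**What to change.** In Section 11.1, Complications/Reoperations:

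1. Specify Kaplan-Meier removal and reoperation curves with 95% confidence intervals, together with retention and reasons for reoperation, for primary augmentation, revision augmentation, primary reconstruction and revision reconstruction. Take indication from enrolment data and name the source field.
2. If an overall rate is reported, compute it as the average of the four curves weighted by enrolled proportions, and label it as such.
3. Add a sensitivity analysis that does not count reoperations whose primary reason is staged reconstruction. The form records a primary reason for each breast, so state the rule for a woman whose two sides differ.
4. State that stratifying removes bias from unequal loss between indications but not informative loss within an indication.

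The cost is a few more tables and wider intervals in the smaller groups. No new data collection is needed if indication was recorded at enrolment.

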### **Complications/Reoperations**

*The cumulative incidence of key local complications (breast pain, infection, rupture, capsular contracture (Baker grades I-IV), explantation, and reoperation) for women with MemoryGel implants will be estimated based on the annual questionnaires as well as the three physician evaluations for the MemoryGel participants using Kaplan-Meier methodology to estimate the time to the first occurrence of the complication or reoperation. Ninety-five percent confidence intervals will be computed. In addition, the relative frequency of reasons for reoperation will be computed.*

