	 Other silicone gel breast implant	_____	
	 Other saline breast implant, cc: _____	_____	
V1 - 14JAN2015		Confidential CRF	
		Page 3	

MENTOR	MGPAS Amendment 2		
 MGPAS Amendment 2 #085 Reoperation (Page 3 of 3) #004			
Participant No:	Site No:	Participant Initials:	REOPERATION
			DataFax Code: 
REOPERATION (Page 3 of 3)			
RIGHT		LEFT	
Mark ALL that apply	Mark ONE primary	Mark ALL that apply	Mark ONE primary
			 Not Done/Not Applicable
REASON FOR REOPERATION (Complication):			
			 Capsular Contracture, mark one Baker Grade:  Grade II
			 Grade III
			 Grade IV
			 Extracapsular Extravasation
			 Hematoma
			 Infection
			 Ptosis
			 Seroma
			 Skin Necrosis
			 Wound Problems
			 Wrinkling/Rippling
REASON FOR REOPERATION (Device Maintenance):			
			 Correction of Asymmetry
			 Device Migration
			 Implant Malposition

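### Section 11.1 gives reasons for reoperation no time axis and no denominator of women at risk, although the second objective asks for reasons over time

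*Combined protocol and SAP*

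**What the plan says.** Section 2.0 sets two questions for the amended study, and both carry a time element. The first is "What are the Kaplan-Meier (KM) implant removal and reoperation rates over time". The second is "What are the reasons for reoperation over time".

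Section 11.1 (Complications/Reoperations) answers the first by "using Kaplan-Meier methodology to estimate the time to the first occurrence of the complication or reoperation", with 95% confidence intervals. For the second it adds one sentence, that "the relative frequency of reasons for reoperation will be computed". The analysis section carried over from the original plan has the same sentence, so the older text adds nothing.

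Section 11.1 also provides for two final reports. The first runs from study start to the end of the Amendment 1 phase. The second is described as "including data from the execution of Amendment 2 to the end of the study". On timing, Section 3.0 states: "The study is currently in year 7 and follow-up will continue through 10 years", or until the national registry opens, if that is sooner.

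The reoperation form in Section 16.0 records the date of each reoperation and, for each breast, every applicable reason, with the instruction "Mark ONE primary". The discontinuation form records a date and a reason, and death is one of the options.

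**The concern.** A relative frequency divides the count for one reason by the count of all reoperations or all reasons. Its denominator holds no women who were followed without a reoperation. It therefore cannot say how likely a woman is to need a reoperation for a given reason, and one reason's share can rise simply because another's falls. Without a time axis it also cannot say when in the life of the implant a reason arises.

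This is one of only two questions left in the amended study. A reader who wants to know whether, for example, suspected rupture becomes a more common cause of reoperation as implants age would not find the answer in the analysis as specified.

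**Working it through.** The plan gives no figure for the reasons analysis, so there is nothing to reproduce. The check sets the objective against the analysis and then shows, with assumed rates, what a share can and cannot convey.

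**1. Objective against analysis**

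- Removal and reoperation rates over time: Kaplan-Meier for first occurrence, with 95% confidence intervals. Time axis and risk set are both present.
- Reasons for reoperation over time: relative frequency only. No interval, number at risk, person-years, counting unit (woman, breast or procedure) or confidence interval is named for the reasons.
- The Kaplan-Meier analysis covers any first reoperation and any first explantation. It is not split by reason, so it does not fill the gap.

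**2. What a share conveys (assumed rates)**

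Take two reasons, each with constant hazard *h* per year. Over *t* years:

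- share of each reason = *h* / (2*h*) = 50%, whatever *h* and *t* are;
- cumulative incidence of each reason = 0.5 × (1 − exp(−2*ht*)).

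Over ten years:

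- *h* = 1%: 0.5 × (1 − exp(−0.2)) = 0.5 × 0.1813 = 9.1%
- *h* = 2%: 0.5 × (1 − exp(−0.4)) = 0.5 × 0.3297 = 16.5%

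Over three years, roughly the span from year 7 to year 10 that the Amendment 2 report could cover:

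- *h* = 1%: 0.5 × (1 − exp(−0.06)) = 0.5 × 0.0582 = 2.9%
- *h* = 2%: 0.5 × (1 − exp(−0.12)) = 0.5 × 0.1131 = 5.7%

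The risk differs almost two-fold and the reported share is 50/50 throughout. The same holds within any single year, so shares tabulated by year would still need the number of women followed beside them.

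**3. Why the number followed cannot be taken as the number enrolled**

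Section 4.0 gives 41,451 MemoryGel participants and a follow-up rate of 21.8% through six years. If that rate is read as a share of those enrolled (an assumption), 41,451 × 0.218 = about 9,036 women. The denominator falls steeply over the years that the question spans.

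**4. What the data allow**

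Reoperation date and primary reason are on the Amendment 2 form, and death and discontinuation dates are on the other form. Section 13.0 provides each site with a list of active and discontinued participants when the amendment starts, which gives a starting count for the risk set. Event-free follow-up after that is not routinely observed, because Section 3.0 collects data only when a reoperation occurs.

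**The case against.** The strongest reply is that the plan is silent, not wrong. A reader might infer that Section 11.1 commits to one figure pooled over all follow-up. It does not: the sentence names no period, and tabulation by year would be consistent with it. This stands, and the point is limited to what the plan fails to specify.

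A reader might also infer that early reoperations would mask late reasons in the Amendment 2 report. The documents do not support that. Enrollment closed on 15 October 2008, the study was in year 7, and that report takes only data from the amendment onward, so reoperations in the first years after implantation do not enter it. The two reports even give a crude early and late split. That split follows the date of the amendment, not years since implantation, and still has no women at risk.

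Third, the question is descriptive, with no control and no test, and a table of reasons by year might be held to satisfy it. In part this is right: such a table would meet the wording. It would not give a risk unless the number of women followed stood beside it.

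Fourth, a cumulative incidence estimate takes more than programming. Amendment 2 data start at about year 7. Under Section 14.0, women discontinued for non-compliance are to be told of the re-consent option when they present for reoperation, so their return can depend on the event. The two breasts may have different primary reasons. The earlier phase's form is not shown, so a primary reason there is unverified. All of this stands and is taken into the fix.

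**Conclusion.** The point holds in a limited form. The plan will show which reasons occur and in what proportion within each report. It does not specify how they change with years since implantation, or at what rate among women at risk. To say that the second objective goes wholly unanswered would be too strong; it is the time element that lacks an analysis.

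The size cannot be taken from the documents, which give no counts by reason. The example shows only that equal shares are compatible with an almost two-fold difference in risk (9.1% against 16.5% over ten years, 2.9% against 5.7% over three), under assumed constant and equal hazards. The Kaplan-Meier objective is unaffected. This is a cheap improvement.

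**What to change.** In Section 11.1:

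- Tabulate first reoperations by primary reason and year since implantation, with the number of women under follow-up in each year.
- Estimate cumulative incidence of first reoperation by primary reason with 95% confidence intervals, treating other reasons and death as competing events (Aalen-Johansen).
- State the time base. Either combine both study phases, after checking that the earlier form records a primary reason, or treat Amendment 2 data as late entry conditional on no earlier reoperation.
- State a woman-level rule for when the two breasts have different primary reasons.
- State who counts as under follow-up when contact occurs only at reoperation, and count women re-consented at a reoperation separately.
- Keep the relative frequency as a supplement, and name its counting unit.

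The cost is some extra programming, a few written rules and a check of the earlier form. No new data field is needed for events under Amendment 2. The remaining weakness is that the risk set will be approximate, and the report should say so.

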## 1.0 INTRODUCTION

On 17 Nov 2006, the U.S. Food and Drug Administration (FDA) approved Mentor's MemoryGel® silicone gel-filled breast implants for use in women who are undergoing primary or revisional breast augmentation and primary or revisional breast reconstruction surgery. The approval was conditional on Mentor conducting a 10-year study designed to collect long-term experience in U.S. women with MemoryGel implants. The MemoryGel Postapproval Study (MemoryGel PAS) is intended to satisfy one element of FDA's postapproval requirements.

As a condition to gaining access to MemoryGel products, physicians were required to sign up for the MemoryGel Gel-Filled Breast implants Post Approval study, and were asked to actively encourage 41,900 women to participate in the 10-year study. In addition, the study included 1,000 women who were undergoing breast implantation with saline breast implants to serve as concurrent controls for assessing rheumatologic and neurologic signs and symptoms.

Approximately 1,700 centers participated in the study and enrollment included 41,451 MemoryGel participants and 1039 saline participants. Study enrollment has been closed since 15 Oct 2008. As of the last annual study report (dated Nov 2013), the follow-up rates through six years were 21.8% for MemoryGel participants and 15.0% for saline participants.

Due in part to the low follow-up rate, which may limit interpretation of the data, FDA in collaboration with the American Society of Plastic Surgeons (ASPS), breast implant manufacturers, and patient representatives have been investigating innovative approaches to collect long-term data on silicone gel breast implants. As part of these efforts, recently, FDA has agreed to changes in the postapproval commitments for the MemoryGel silicone gel-filled breast implants that include changes to MemoryGel PAS. These changes are described in this amended protocol.

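### On the natural reading, no final report gives first-reoperation and explantation rates from implantation to study end, and the Amendment 2-only Kaplan-Meier figure has no defined estimand

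*Combined protocol and SAP*

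**What the plan says.** Section 2.0 keeps two questions under Amendment 2. One is "What are the Kaplan-Meier (KM) implant removal and reoperation rates over time"; the other concerns reasons for reoperation.

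Section 11.1 (Complications/Reoperations, Amendment 2 text) estimates cumulative incidence from physician evaluations, using "Kaplan-Meier methodology to estimate the time to the first occurrence of the complication or reoperation". It then lists two final reports to FDA:

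- Report 1: "including data from beginning of the study through the end of the study phase under Amendment 1", analysed by the original plan.
- Report 2: "including data from the execution of Amendment 2 to the end of the study", analysed by the Amendment 2 text.

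Section 3.0 gives the timing: "The study is currently in year 7 and follow-up will continue through 10 years", or until the national registry opens if that is sooner. Enrollment closed on 15 Oct 2008. On ascertainment, the same section says: "Data collection will only take place if a participant requires a secondary procedure/reoperation".

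Section 5.0 (Study Evaluations) notes that the reoperation data were already being recorded under the original protocol. Section 14.0 offers re-consent to women previously discontinued for non-compliance. The only occasion it describes for telling them so is when they present for a further procedure.

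**The concern.** A Kaplan-Meier curve for time to first event needs a time origin, a rule for when each woman joins the risk set, and a rule for women who have already had the event. Section 11.1 states none of these for a report whose data begin years after every participant's implantation. Early events fall in one report and late events in the other, and no analysis is planned that joins them.

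This affects one of only two remaining objectives. The original approval was "conditional on Mentor conducting a 10-year study designed to collect long-term experience". A reader who finds a cumulative incidence in the Amendment 2 report could take it as the risk since implantation, when it would describe only the last few years.

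**Working it through.** **1. The two reports side by side (section 11.1).**

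| | Report 1 | Report 2 |
|---|---|---|
| Starts | Beginning of study | Execution of Amendment 2 |
| Stops | End of Amendment 1 phase | End of study |
| Source for reoperation | Annual questionnaires and three physician evaluations | Physician evaluations only |
| Runs from implantation to study end? | No, stops early | No, starts late |

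No other section plans a combined analysis. Section 7.0 puts all data into the annual reports but specifies no curve.

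**2. How late is entry?** Section 3.0 says study year 7. Even at the Nov 2013 annual report that the amendment cites, the last woman enrolled (15 Oct 2008) was about 5.0-5.1 years in. In the Amendment 2 window nobody is at risk in the early years, so those data alone cannot yield risk from implantation.

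**3. What could report 2 estimate?** There are two possibilities:

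- If women with an earlier event are excluded, it is a risk conditional on being event-free at entry.
- If they stay in, it is the first event within the window in a mixed population.

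Neither is cumulative incidence from implantation, and the text does not choose between them.

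**4. Illustrative size of the late-window risk.** The documents give no reoperation rate or hazard shape, so both are assumed. With 10-year incidence F and Weibull shape k, cumulative hazard is H(t) = -ln(1-F) x (t/10)^k. The risk from entry at year L to year 10, given event-free at L, is r = 1 - exp[-(H(10) - H(L))].

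- F = 0.20, k = 0.5, L = 7: H(10) = 0.2231, H(7) = 0.2231 x 0.8367 = 0.1867, r = 1 - exp(-0.0364) = 3.6%.
- F = 0.45, k = 1.0, L = 7: H(10) = 0.5978, H(7) = 0.4185, r = 1 - exp(-0.1794) = 16.4%.

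Across F = 20-45% and k = 0.5-1.0, r is 3.6-16.4%, or 0.18-0.36 of the 10-year figure. At a mid-range case (F = 0.32, k = 0.7), r = 8.2% for entry at year 7, 13.8% at year 5 and 5.4% at year 8. Chaining recovers the full value: 0.7405 x 0.9183 = 0.68 = 1 - 0.32. These runs go to year 10; an earlier registry stop would shorten the window.

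**5. Entry at the event.** Let a be the share of women still active, d = 1 - a, and p and q the re-consent shares among reoperated and event-free discontinued women. The apparent risk is (a r + d r p) / (a + d r p + d(1 - r) q). With assumed a = 0.3, p = 0.25 and r = 0.0817:

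- q = 0 gives 12.3%
- q = 0.125 gives 9.8%
- q = 0.25 gives 8.2%, no bias

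The bias therefore depends wholly on whether event-free women re-consent less often.

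**6. Censoring rule for a linked curve.** Let c be the share of late reoperations reported and g the share of event-free active women with a dated end-of-study form. Assume c = 0.5.

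- Carrying silent women event-free to study end gives c r = 4.1% in the window. The year-10 value is then 1 - 0.7405 x 0.959 = 0.290, against an assumed true 0.320.
- Censoring at last contact gives c r / [c r + g(1 - r)]. This is 100% at g = 0 and 15.1% at g = 0.25.

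Because contact under Amendment 2 is triggered by reoperation, g near zero is plausible and last-contact censoring can fail badly.

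**The case against.** Several points on the other side are fair.

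- *The wording does not forbid linkage.* The text says what each report includes, not what it is limited to. The Amendment 2 forms in section 16.0 show no implantation date, so any curve timed from implantation must draw on earlier records. That stands as a reason for caution. However, the two bullets have matching start and end points, and no joined analysis appears anywhere. If linkage is intended, one sentence would settle it.
- *Separate reports suit a change in ascertainment.* Questionnaires and scheduled visits have ended, so keeping the phases apart is defensible. This argues for marking the change on the curve and labelling each estimate, not for omitting the linked curve.
- *FDA agreed to changed commitments* (section 1.0), so the original 10-year condition does not prove that a full curve is still required. That is correct. The point rests on the section 2.0 objective, which survives the amendment.
- *Follow-up is poor.* Section 4.0 reports that "the follow-up rates through six years were 21.8% for MemoryGel participants"; if the denominator is all enrolled women, that is 0.218 x 41,451, or about 9,036. Late estimates will be weak under any method. This limits precision and credibility, but does not excuse an undefined estimand.

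**Conclusion.** The point holds and is worth fixing. Read naturally, the plan yields no final-report estimate from implantation to study end for a remaining objective, and the Amendment 2-only estimate has no stated origin, entry rule or prior-event rule. This rests on reading the two data descriptions as report windows.

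Three stronger inferences are not supported:

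- A reader might infer that the Amendment 2 figure *is* conditional on being event-free at entry. Section 11.1 excludes nobody with an earlier event, so that is only one of two possibilities.
- A reader might infer a known bias. Event-triggered re-entry pushes the figure up and incomplete reporting pushes it down, so the net direction is not fixed.
- A reader might take 3.6-16.4% as an estimate for this cohort. It shows only how far a late-window risk can lie from a 10-year one under assumed rates, assumed shapes and entry at year 7.

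**What to change.** Amend section 11.1 so that the Amendment 2 final report adds a linked curve:

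- Use all MemoryGel data, linked by participant number, with time zero at implantation, and count the first event in either phase. Run it to actual study end, meaning year 10 or registry opening, whichever is first.
- Mark the start of Amendment 2 on the curve and state the change from questionnaires plus physicians to physicians only. Show a physician-only version alongside for consistency.
- Do not let re-consented women enter the risk set at their event; report those events separately.
- For the Amendment 2 part, show active women carried event-free to study end, labelled a likely lower bound if reporting is incomplete. Do not make last-contact censoring the main rule.
- If an Amendment 2-only estimate is kept, use delayed entry, exclude women with a prior event, and label it conditional on being event-free at entry.

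The cost is protocol and SAP wording, a merged dataset and some extra analysis. No new data collection is needed. The late part of the curve will stay uncertain because of the changed ascertainment and low follow-up.
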